6.2 Investigational product

6.2.1 Investigational product description

Tolvaptan is provided as tablets. Metformin is provided as coated tables.

6.2.2 Packaging and labeling

All IMP will be provided to the investigator(s) by the promoter of the Coordinating Center or designated agent.

Tolvaptan (Jinarc®) will be provided as 3 types of packages:

1) package containing 4 blisters of tolvaptan. Each blister contains 14 tablets: 7 15 mg tablets (triangular, in a green background), and 7 45 mg tablets (squared, in a gray background);

2) package containing 4 blisters of tolvaptan. Each blister contains 14 tablets: 7 30 mg tablets (rounded, in a purple background), and 7 60 mg tablets (rectangular, in a golden background);

3) package containing 4 blisters of tolvaptan. Each blister contains 14 tablets: 7 60 mg tablets (rectangular, in a golden background); and 7 90 mg tablets (pentagonal, in an orange background).

Metformin (Zuglimet®) will be provided as a package containing 3 blisters. Each blister contains 10 500 mg tablets.

Each package used will be labeled to clearly disclose the subject identification number (ID), compound ID, trial number, Promoter's name and address, instructions for use, route of administration.

Each package of the designated IMP will be dispensed at the beginning of each specific period.

For the tolvaptan titration period and subsequent run-in, subjects will receive 2 cartons at the first visit of tolvaptan 45/15 mg.

6.2.3 Storage Conditions

All IMPs will be stored in a securely locked cabinet or enclosure. Access will be limited to investigators and their designees. Neither investigators nor any designees may provide IMP to any subject not participating in this protocol.

The IMP should be stored according to the conditions specified in the IMP label. The clinical site staff will maintain a temperature log in the drug storage area recording the temperature at least once each working day.

6.2.4 Administration Method

IMP will be distributed to the patient during each visit it is expected drug dispensation. Patient will orally take IMP at home.

6.2.5 Treatment of Overdose

In case of overdose, the subject will be instructed to interrupt IMP assumption, skipping the same number and type of doses he has over-assumed.

If the patient has assumed twice the scheduled maximum daily dose, it also will be reported as IRE. An out of protocol visit has to be scheduled and the subject will undergo blood withdrawal in order to assess any AEs. IMP assumption can be restarted if no AE has arisen.

6.2.6 Retrieval and/or Destruction

The investigator or designee must maintain an inventory record of IMP received, dispensed, administered, and returned.

Upon completion or termination of the trial, all unused and/or partially used IMP must be returned to the sponsor or a designated agent.

All IMP returned to the sponsor must be accompanied by appropriate documentation and be identified by protocol number with trial site number on the outermost shipping container. Returned supplies should be in the original containers. The assigned trial monitor will facilitate the return of unused and/or partially used IMP.

6.3 Prohibited medications and dietary restrictions

Medications or surgical therapies used for the purpose or potential for modifying the progression of PKD cyst growth or development will be prohibited. These include, but are not restricted to, somatostatin agonists, rapamune (sirolimus), anti-sense ribonucleic acid (RNA) therapies, vasopressin antagonists, (mozavaptan), Vaprisol (conivaptan), or agonists (e.g., desmopressin) and cyst decompression surgery.

Continuous or short-term use of other medications, while not prohibited, may be restricted by the investigator because of their potential for interference with metabolism or efficacy endpoints. This includes the use of diuretics which may be used intermittently. Diuretics are not generally recommended in ADPKD due to their tendency to increase AVP levels through relative dehydration or volume depletion; thus, chronic use of diuretics (e.g., for hypertension) will be prohibited due to potential endpoint interference and is an exclusionary criterion for this trial. Subjects taking such agents must first sign an ICF and then agree to be switched to an alternate form of therapy in order to be eligible for the trial. Some drugs are known to alter creatinine concentrations so, while not prohibited, subjects should alert their trial doctor, and any other health-care providers, to take this into consideration when considering changes in their prescribed or over-the-counter medications. A brief list would include: cimetidine, NSAID medications like aspirin or ibuprofen, chemotherapy drugs, and cephalosporin, RAAS blockage, acarbose, guar gum, phenprocoumon, oral anticoagulants, thrombolytic drugs, ranolazin, cephalexin.

Since tolvaptan is a weak cytochrome P450 (CYP) 3A4 substrate, potent CYP3A4 inhibitors should be avoided during the trial, with the exception of amiodarone, which was found to have no effect on tolvaptan. A partial list of other CYP3A4 inhibitors include pomelo, grapefruit, or Seville orange and drugs listed in table 1.

Restriction of excess dietary sodium and cooked meat protein may prove beneficial to subjects with a history of, or predisposition for, hypertension or kidney disease in general

47

and should be applied to all subjects diagnosed with advanced ADPKD, particularly if there is evidence for a tendency towards rapid progression. In the absence of alternate regional practices, restrictions of dietary salt < 5g/day and dietary cooked meat protein < 1 g/kg/day and to limit caffeinated drinks/foods should also be given (no more than 2 coffee equivalents per day).

Additionally, fluid intake is generally encouraged in subjects with PKD. Given the potential for dehydration with tolvaptan treatment, all subjects should be instructed to ingest fluids in anticipation of, or at the first sign of thirst in order to avoid excessive thirst or dehydration. Upon consent, all subjects should receive the recommendation to ingestion of at least 2-3 liters of fluid (including in solid, semi-solid, and liquid foods) per day, unless otherwise directed by your study doctor. This recommendation should start during screening and continue through the end of the trial. Additionally, subjects should ingest 1 to 2 cups of water before bedtime regardless of perceived thirst and replenish fluids overnight with each episode of nocturia. Dehydration will be monitored by subject self-assessment of changes in body weight and reporting of symptoms. Acute changes of > 3% of body weight (increase or decrease) over any 7-day period should be noted.

7. STUDY DURATION

7.1 Study Duration

The trial has a 36 months overall duration, that include a 9 months recruitment period.

7.1.1 Screening Period:

Has a 2 weeks duration, it is included in the 9 months recruitment period.

7.1.3 Treatment Period:

It has a 25 months duration. Each month lasts 28 days. It includes the 3 weeks titration period and the 1 week run-in period.

7.1.4 Post-Treatment Follow-up Period:

It lasts 21 days.

7.1.4 Total Study Duration:

About 3 years.

8. STUDY ENDPOINTS

Trial endpoints were constructed based on advice obtained at scientific advisory boards and meetings with regulatory agencies from Japan, EU and the USA and were chosen to represent potentially clinically meaningful changes in levels of laboratory or physiological parameters and patient symptoms reasonably expected to develop or worsen with progressive ADPKD.

8.1 Effectiveness Endpoints

8.1.1 Primary Endpoint

Primary outcome of the study is to evaluate the *difference between Metformin and Tolvaptan in annualized slope of eGFR (CKD-EPI) for individual subjects*, that will be calculated using an appropriate baseline and post-randomization assessment. Traditionally, the primary endpoint in trials testing renoprotective effects of interventions has been the incidence of ESRD or doubling of serum creatinine, which correlates to a 57% reduction in eGFR. Of note, ADPKD is a relatively slowly progressive disease. In a population such as that of the TEMPO 3:4 trial, which was selected to have early-stage ADPKD (eGFR >60 mL/min), it cannot be expected that this endpoint will occur within the typical duration of a renal trial. Adopting this endpoint would therefore only pick up cases

of acute kidney injury and not be of help for studying the effect of interventions on progression of the disease itself. To stimulate progress in developing renoprotective agents, especially for studies in early-stage CKD and diseases that are relatively slow in progression, the nephrological community has pleaded for the use of alternative endpoints for renal trials, namely lesser declines in eGFR. Regulatory authorities have accepted this proposal. When studying the incidence of a 25% reduction in eGFR [a priori defined in the TEMPO 3:4 trial and accepted by the European Medicines Agency (EMA)], there was a significant 61% relative risk reduction with tolvaptan (number needed to treat to prevent one event was ~11). One of the inclusion criteria for the pivotal TEMPO 3:4 trial was a creatinine clearance as estimated with the Cockroft-Gault equation ≥60 mL/min/1.73 m2. Due to tubular creatinine secretion, creatinine clearance overestimates GFR by ~20%. Consequently, the TEMPO 3:4 trial included a considerable number of ADPKD patients (n = 247; 17%) with an eGFR, as determined by the Chronic Kidney Disease Epidemiology Collaboration (CKD-EPI) equation, of <60 mL/min/1.73 m2. A post hoc analysis indicated that in these patients, treatment efficacy was similar or even slightly better than in those with higher eGFR. However, the number of patients with CKD stage 3b, i.e. an eGFR of 30-45 mL/min/1.73 m2, was small.

8.1.2 Secondary Endpoints

The key secondary endpoint is *the percent change from baseline in htTKV as measured by CT-scan at 24 months*. The use of htTKV as a surrogate biomarker for progression of ADPKD is supported by the Consortium for Radiologic Imaging Study of Polycystic Kidney Disease (CRISP) which showed that baseline TKV strongly predicts subsequent loss of GFR. TKV is now widely used in RCTs for ADPKD.

Other secondary efficacy end-points include:

- Difference in rate of albuminuria change;

- Difference in rate of urological events and of hypertension onset (for not hypertensive patients at baseline);
- Hypertension worsening or amelioration (for those who are hypertensive);
- Exploratory efficacy Outcomes (changes from baseline in urinary EGF and EGF/MCP-1 levels).

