Randomization visit will occur on Day -29. During this visit patients will be randomized (in a ratio 1:1 tolvaptan:metformin) to each arm of treatment and will start an **IMP titration period** (3 weeks from -28 to -8). Subjects not tolerating the minimum IMP dose will be considered "Titration failures" and will complete End of Treatment (EoTx) visit assessments and will be followed up after 7 days by phone call to assess any ongoing AEs. Subjects tolerating the minimum IMP dose enter the unblind **run-in period** (1 week from Day -7 to -1). During the "Run-in" phase, subjects will continue on a stable IMP dose to confirm tolerability over a longer period. At the end of the run-in period (Day -1), subjects not tolerating the minimum IMP dose will be considered "Run-in failures" and will complete EoTx visit assessments and will be followed up after 7 days by phone call to assess any ongoing AEs. Subjects completing the run-in will start the open-label **24 months treatment period**, during which visits will be collected three-monthly. At the end of the 24th month, and in case of early treatment cessation, **follow-up period** (3 weeks from +8 to +21) will start, during which 2 visits have to be collected. No IMP will be administered during this period.

Assessments at the Randomization (Day -29), End of IMP Run-in Period (Day -1), End of each three-monthly of on-therapy period will include those for points 2 to 8 of screening period plus IMP dispensation.

Assessments during EoTx Visits (in case of Titration failure, Run-in failure, early treatment cessation) and Follow-up visits will include those for points 2 to 8 of screening period. Non contrast enhanced CT-scan of the kidneys for TKV measurement will be also performed at the end of Month 24.

Patients treated with tolvaptan, will anyhow undergo monthly visits during the first 18 months of therapy (as prescribed by the additional monitoring requested by AIFA), then every three months.

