4.5 Unblind Treatment Period (Day 0 to Month 24)

Only subjects completing the IMP run-in period tolerating at least 45/15 mg of tolvaptan and 500/500 mg of metformin will be allowed upon entry to this unblind period.

In the metformin arm, during the treatment period visits will be scheduled every 3 months (each month has 28 days duration), within 3 days of the end of the trimester.

In tolvaptan treated patients, visits will be performed every month for the first 18 months, then every three months (each month has 28 days duration), within 3 days of the end of the month or the trimester (as prescribed by the additional monitoring requested by AIFA).

Beside the clinic visit and dispensing new bottles of IMP, subjects will have blood drawn on the last day of this period for efficacy and safety measures. The treatment duration of these subjects will be 24 months from the end of IMP run-in. Subjects not continuing in this trial will complete EoTx visit assessments and be followed for 7 days to assess any ongoing AEs.

From that point forward, every effort to maintain adherence and continuation of the subjects until the end of the trial should be undertaken. If continued tolerability becomes an issue, subjects may temporarily interrupt treatment as needed.

All subjects have the right to withdraw their consent from further participation in the trial at any time without prejudice.

Regardless of discontinuation of IMP, the subjects are expected to complete all monthly visits and assessments including the Month 24 visit.

4.6 Follow-up Period (up to Day +21 since Month 24 or End of Treatment)

Randomized subjects will enter the follow-up period after they complete the unblind, randomized treatment period, or after their EoTx visit, if they discontinued IMP. The follow-up period will be for 21 days in duration.

There will be no scheduled visits/assessments during the first week of the follow-up period. After the first week, 2 visits should be scheduled during the remaining 2 weeks of the follow-up period (between Day +8 and Day +21). The first visit should be scheduled on approximately Day +8, the second visit on approximately Day +21. These visits will be clinic visit.

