9.1.4 Treatment Period

Assessment at each on-treatment visit will include:

1) Perform physical examination, including post-void body weight and height;

2) Record medical/PKD history;

3) Record concomitant medications and ensure subject's treatment meets current standard of care including lifestyle and dietary recommendations, especially for ingestion of at least2-3 liters of fluid per day as appropriate, unless otherwise directed by study doctor;

4) Assess AEs, if reported;

5) Assess vital signs (include heart rate and blood pressure);

6) Serum pregnancy test for WOCBP;

7) Collect urine and blood samples for clinical laboratory analyses, including serum creatinine, liver function tests, glucose metabolism parameter, CBC and venous gas analysis;

8) IMP dispensation;

9) IMP reconciliation (subjects must return any unused IMP);

10) Non contrast enhanced CT-scan of the kidneys for TKV measurement (at the end of month 24).

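### The plan gives two conflicting blood-pressure schedules for tolvaptan (20 or 8 on-treatment readings, against 8 on metformin) and no rule on which readings count; if the monthly ones are used, hypertension onset would be found more often or earlier on tolvaptan without any drug difference.

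*Combined protocol and SAP*

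**What the plan says.** Two of the other secondary efficacy endpoints in section 8.1.2 concern hypertension: "Difference in rate of urological events and of hypertension onset (for not hypertensive patients at baseline") and "Hypertension worsening or amelioration (for those who are hypertensive"). Neither comes with a threshold, a number of readings or a confirmation rule.

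The visit schedule differs by arm. Section 4.5 states "In tolvaptan treated patients, visits will be performed every month for the first 18 months, then every three months", and "In the metformin arm, during the treatment period visits will be scheduled every 3 months". On duration it says "The treatment duration of these subjects will be 24 months from the end of IMP run-in". Section 4 repeats the difference: "Patients treated with tolvaptan, will anyhow undergo monthly visits during the first 18 months of therapy".

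Section 9.1.4 opens its list with "Assessment at each on-treatment visit will include", and item 5 is "Assess vital signs (include heart rate and blood pressure"). It makes no exception for the extra tolvaptan visits.

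Other places point to a common schedule:
- Section 4 ties the screening list, which includes vital signs, to the end of each three-month period on therapy.
- Section 10.4 says blood pressure is taken at the visits in the Schedule of Assessments. Section 10.3 identifies that schedule as Figure 1.
- Figure 1 is one table for both arms. On treatment it marks blood pressure at Months 3, 6, 9, 12, 15, 18, 21 and 24 only.

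Section 12.3 names a model for eGFR slope and TKV. It has no rule for the hypertension endpoints and none limiting a comparison to visits that both arms share.

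**The concern.** A site that follows sections 4.5 and 9.1.4 will record blood pressure monthly on tolvaptan for 18 months and every three months on metformin. Unless onset is tied to shared visits, tolvaptan patients have more opportunities to show a raised reading, and a true onset is noticed sooner. The comparison would then partly reflect the visit schedule, in the direction that favours metformin.

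The trial is open label, and section 12.3 calls any P value below 0.05 significant with no allowance for multiple endpoints. An artefact of the schedule could therefore be reported as metformin protecting against hypertension.

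**Working it through.** The plan states no number of readings per arm and no expected hypertension rate, so it has no figure of its own to reproduce.

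**Step 1: count the occasions.**
- Sections 4.5 and 9.1.4: tolvaptan has Months 1–18, then 21 and 24, so 18 + 2 = 20. Metformin has 24/3 = 8. The ratio is 20/8 = 2.5. All 8 metformin visits are also tolvaptan visits, so 20 − 8 = 12 tolvaptan occasions (60%) have no metformin counterpart.
- Section 4 (three-monthly assessments), section 10.4 and Figure 1: 8 against 8.

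**Step 2: can the documents settle which count applies?** They cannot.
- Figure 1 is not the full tolvaptan schedule. It has no monthly columns and shows AST and ALT only three-monthly on treatment, whereas section 10.5 requires transaminases at each monthly tolvaptan visit.
- Section 9.1.4 is not a reliable literal list either. It puts height and complete blood count at every on-treatment visit, whereas Figure 1 has height at the first screening visit only and the blood count at five of the eight on-treatment visits.

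**Step 3: size under 20 against 8, with no drug effect and no true onset.** All blood-pressure inputs are assumptions: usual systolic pressure normal with mean 122 and SD 8, truncated below 135; visit-to-visit SD 8, 10 or 12; threshold 140. Simulation of 400,000 patients:

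| Visit SD | Any high reading, tolvaptan v metformin | Two consecutive high readings, tolvaptan v metformin |
|---|---|---|
| 8 | 33% v 20% | 5.7% v 2.4% |
| 10 | 50% v 31% | 10.7% v 4.8% |
| 12 | 64% v 43% | 16.6% v 7.6% |

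The ratio is about 1.5–1.7 for any reading and 2.2–2.4 for two consecutive readings. Confirmation lowers the absolute excess but not the ratio.

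**Step 4: a simpler cross-check.** Let q be the assumed chance of a spurious raised reading at one visit, with visits independent. The chance of at least one in k visits is 1 − (1 − q)^k.
- q = 0.5%: 9.5% (k = 20) v 3.9% (k = 8).
- q = 2%: 1 − 0.98^20 = 33.2% v 1 − 0.98^8 = 14.9%.
- q = 10%: 87.8% v 57.0%.

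With within-patient correlation 0.5 and a cut-off exceeded about 2% of the time, any reading gives 16.8% v 9.5%, and two consecutive readings 2.6% v 1.2%.

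For the independent case at q = 2%, a two-proportion comparison would be falsely significant with probability about 0.75 at 75 non-hypertensive patients per arm and 0.32 at 25 per arm. At q = 0.5% the figures are 0.28 and 0.12. The plan does not give the number non-hypertensive at baseline; 75 is the ceiling if 150 are randomised 1:1.

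**Step 5: permanent onset, read without error.** The proportion found by Month 24 is then the same in both arms and only timing differs. With 28-day months, the mean wait to the next visit during Months 1–18 is 28/2 = 14 days on tolvaptan and 84/2 = 42 days on metformin. With onset uniform over 24 months, the mean delay is (18 × 0.5 + 6 × 1.5)/24 = 0.75 months against 1.5 months.

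**Step 6: after restriction to shared visits.** Occasions are 8 v 8, and at q = 2% the chance of a spurious raised reading is 14.9% in each arm.

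**The case against.** The strongest reply is that the imbalance may not exist. Section 10.4, the section on vital signs, points to Figure 1, which gives both arms the same eight on-treatment readings, and section 4 says much the same. For the monthly tolvaptan visits, section 10.5 names only transaminase testing. This stands to the extent that 20 against 8 is one of two readings. A reader might infer from section 9.1.4 that onset will certainly be over-detected on tolvaptan; the documents do not support that. Nor do they exclude it, since Figure 1 omits monthly tests that section 10.5 requires.

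A second reply is that the excess depends on an onset rule the plan does not contain. That also stands. The percentages above follow from assumed pressures and a chosen threshold, and for permanent onset read without error the Month 24 proportions agree.

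A third reply is that hypertension may be captured as a diagnosis or adverse event. Section 10.1 lists it among events that are endpoints, and section 9.1.6.3 collects PKD outcomes monthly in both arms. This would soften the imbalance for reported diagnoses. It would not equalise measured pressures, because those contacts may be by telephone, and extra clinic visits can still bring a diagnosis forward.

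It is also tempting to extend the argument to worsening or amelioration and to vital signs generally. That goes too far: extra readings create more chances to record either worsening or amelioration, and more frequent measurement does not by itself shift a mean change.

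**Conclusion.** The point holds in conditional form. The plan contains two incompatible blood-pressure schedules for the tolvaptan arm and does not say which readings define the hypertension endpoints. If the monthly tolvaptan readings are used, the bias in onset runs against tolvaptan. Under the assumed systolic distribution its size is about 33–64% against 20–43% for any high reading, and about 6–17% against 2–8% for two consecutive high readings. If onset is permanent and measured without error, the effect reduces to earlier detection. The direction for worsening or amelioration is undetermined, and no bias is shown for mean vital-sign change.

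The visit counts come from the documents; every percentage rests on stated assumptions. These are neither the primary nor the key secondary endpoint, but the change is worth making because it is specific and nearly free.

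**What to change.** 1. Reconcile section 9.1.4 with section 4, section 10.4 and Figure 1, so that the plan states one blood-pressure schedule for each arm.
2. In sections 8.1.2 and 12.3, define hypertension onset and worsening or amelioration: threshold, number of readings, confirmation rule, and how a reported diagnosis counts.
3. In the same place, state that for the between-arm comparison both endpoints are derived only from the visits common to both arms (Months 3, 6, 9, 12, 15, 18, 21 and 24), with onset dated to the three-monthly visit. Any readings from the additional tolvaptan visits stay in the database for patient care and safety.

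The cost is a few sentences and no new data. There are two small downsides. Interim tolvaptan readings are not used in this comparison. The rule also cannot undo antihypertensive treatment started after an interim reading, which should be reported as a limitation.
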